4.1 Criteria for identifying potentially eligible patients

Patients will be considered potentially eligible for the trial if they meet the following criteria:

- a. COPD diagnosis
- b. Aged 35 or over
- c. Current smoker (when identifying patients through search of medical records this will only be applied if there is relatively complete and recent data available on smoking status.)

4.2 Identification by research site

At the site, potentially eligible patients will be identified either by their direct care team or by the patients asking for/accessing trial information after seeing ethically approved advertising in clinical areas and/or websites and/or social media accounts. Those identified will either be directed to the site trial team who will conduct the pre-baseline check on the ECAL database and book the patient into a baseline appointment or they will have access to an invitation pack which may be on paper or online, or they can email or call BCTU directly.

In addition, the secondary care site team can identify potentially eligible patients through clinic lists/hospital records based on the criteria outlined in section 4.1, and those identified will be invited to take part in the trial, by their direct care team. This may be by phone, post (paper invitation pack) or by email/text (online invitation pack). Details of the invite process can be found in section 4.4.

4.3 Identification by PIC

Potential participants will be identified through centres (e.g. GP practices, pulmonary rehabilitation, targeted lung health check/ lung cancer screening) within a reasonable distance from participating research sites. The PIC will conduct clinic list/medical record system search(es) to identify potentially eligible patients based on the criteria outlined in section 4.1. The list(s) will be screened for potentially eligible patients to exclude those patients considered inappropriate to be invited to participate in the trial. Potential eligible patients will then be contacted by the PIC to invite them to take part in the trial. This invite may be by post or text and will provide an invitation pack which may be on paper or online, as appropriate for the contact method. Details of the invite process can be found in section 4.4.

In addition, the trial will be advertised using ethically approved promotional materials (i.e. posters and flyers) in the waiting rooms and/or websites and/or social media accounts of participating PIC. Patients who are interested in the trial will be able to express their interest by accessing the online invitation pack using the link provided or can contact the trial office directly via email or phone.

4.4 Identification by self-referral

The trial will be advertised/ promoted to members of the public using local/social media campaigns, Be Part of Research Volunteer Service (BPORVS) and wider care settings, i.e. community organisations (i.e. breatheasy groups) and charities. People who are interested can self-refer by completing either an online or paper reply slip or contacting the trial office directly via email or phone.

A mixture of all the recruitment methods specified above will proceed in parallel until the required sample size is reached.

4.5 Patient invitation to take part

Patients will receive either:

- a. **Paper invitation pack** that will contain the trial invitation letter, Summary Participant Information Sheet (PIS) with link to the main PIS, reply slip and pre-paid return envelope.
- b. **Online versions of invitation pack** that will contain access to the summary PIS, main PIS and a reply slip that can be returned electronically

Reply slips will collect the patients name and contact details and will be returned to BCTU. BCTU will then contact the patient to complete the baseline check and book patients into the baseline appointment (see section 4.5.2).

Where patients are approached face to face at site and are able to speak directly to the site trial team, or express an interest directly to BCTU, a consent to contact CRF will be completed (instead of a reply slip) and the patient will be given access the PIS either in paper or online, as appropriate as part of the pre-screening check (see section 4.5).

For patients sent an invitation by primary or secondary care after identification through medical records or clinic lists, a reminder invitation letter, text or call will give approximately 2 weeks after the initial invite. All potential participants identified in this way will receive the reminder regardless of whether or not they have returned their reply slip or expressed an interest directly. This will be made clear in the main PIS. The reminder invitation will acknowledge those who have already responded and ask them to ignore the reminder. If no response is received after this, the patient will be considered as not interested and will not be contacted again.

4.6 Strategy to improve inclusion

To enhance the trial's inclusivity, the trial team will offer access to a translation service (available by telephone, video, or in person) to assist with providing study information and behavioural support, in addition to questionnaire completion and data collection. Use of NHS translation services may be utilised at sites as needed. Additionally, participants are welcome to seek assistance from a friend or family member, if preferred.

4.7 Pre-baseline check and baseline appointment booking

Patients expressing an interest in the trial will proceed to a pre-baseline check and will have their baseline appointment booked if they pass the check. The purpose of the pre-baseline check is to reduce the chance of baseline appointments being scheduled for patients who are ineligible.

4.7.1 Conducted by research sites

Patients who are identified face to face at research sites will proceed straight to the pre-baseline check and baseline appointment booking at the site if they are able to. The information provided will be entered straight onto the ECAL database. This process will not involve BCTU.

The BCTU trial office may also allocate reply slips to a relevant site so the pre-baseline check and baseline appointment booking can be undertaken by site.

The pre-baseline check will include the following:

- a) Provide the participant with the summary PIS and check they are interested in taking part
- b) Discuss the trial with the patient
- c) Answer any questions the patient has about the trial

-
- d) If the patient is interested, complete a consent to contact form which will add the patient's contact details to the ECAL database (this is instead of the patient completing a reply slip as part of the invitation pack)
 - e) Go through the pre-baseline check criteria within the ECAL trial database (see section 4.6.3)
 - f) If eligible based on pre-baseline check, book the patient directly into the baseline clinic. Notify the patient of their baseline appointment date/time, i.e. verbally, appointment card, SMS text, email or letter
 - g) Upon booking a baseline visit, the patient will be directed to view the main PIS on the trial website so they have time to read through ahead of their appointment.

4.7.2 Conducted by BCTU or QMUL

When a reply slip has been received by BCTU, or potentially eligible patients have contacted BCTU directly and a consent to contact CRF has been completed, the information will be entered on to the ECAL database. As the patient has actively opted to return the reply slip or express an interest directly and provided their name and contact information on it, this indicates consent for BCTU to contact them. It will explicitly state on the reply slip and consent to contact CRF that the patient's details will be stored on the ECAL database once received by BCTU.

BCTU or QMUL team will then contact the patient for the pre-baseline check. During the pre-baseline check, BCTU or QMUL will:

- a) Discuss the trial with the patient
- b) Answer any questions the patient has about the trial
- c) Check that they are interested in taking part
- d) Go through the pre-baseline check criteria within the ECAL trial database (see section 4.5.1)
- e) If eligible based on pre-baseline check, book the patient into a baseline visit at their nearest participating research site (or their choice of site)
- f) Notify the relevant site and request a baseline appointment booking (site are responsible for informing the patient of their baseline appointment date/time, i.e. verbally, appointment card, SMS text, email or letter)
- g) Patients will be directed to view the main PIS on the trial website so they have time to read through ahead of their baseline appointment

4.7.3 Pre-baseline check criteria

The pre-baseline check will check that patients meet the minimum trial entry criteria:

- a) Confirmation of COPD status
- b) 35+ years old
- c) Currently daily smoking
- d) Motivated to stop smoking
- e) Not currently taking part in another trial of COPD treatment/ management or smoking cessation
- f) Check if patients have had an COPD exacerbation or inpatient hospital stay within the last 8 weeks and/or Contraindications to spirometry within the last 12 weeks

For criteria g, if a patient answers yes to any of these the baseline visit will be made when enough time has passed for them to be eligible (see exclusion criteria, section 6.2).

Where a patient is found to be unsuitable for a baseline visit as they have not met criteria a-f, their database record will be archived to be no longer accessible by the trial team and if applicable, their paper reply slip will be confidentially destroyed.

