7.1 Randomisation process

After informed consent has been received, eligibility has been confirmed, and baseline assessments have been completed, the participant can be randomised into the trial using the REDCap trial database (see section 10.3 for baseline procedures).

Randomisation will be provided via the trial database using a secure online system (available at <https://bctu-redcap.bham.ac.uk>), thereby ensuring allocation concealment. Unique log-in usernames and passwords will be provided to those who wish to use the online system and who

have been delegated the role of randomising participants into the trial as detailed on the ECAL Site Signature and Delegation Log. These unique log-in details must not be shared with other staff and in no circumstances should staff at sites access either system using another person's login details. The online system will be available 24 hours a day, 7 days a week, apart from short periods of scheduled maintenance which sites will be informed of in advance.

In the event of the online system not being available, a back-up telephone toll-free randomisation service ([name]) is available Monday to Friday, 09:00 to 17:00 UK time, except for bank holidays, government guided closures and University of Birmingham closed days.

Participants will be randomised at the level of the individual in a 1:1 ratio to either the intervention (EC) or comparator (NRT). A minimisation algorithm will be used within the online randomisation system to ensure balance in the treatment allocation over the following key potential confounding variables:

- COPD stage (levels: stage 1-2 and stage 3- 4 based on FEV₁)
- Age (levels: 35-65, 66+ years)
- Sex at birth (levels: male, female)
- Fagerstrom test for nicotine dependence (FTND) score (levels: ≤6, 7+)

To avoid the possibility of the intervention allocation becoming predictable, a random element will be included in the algorithm. Full details of the randomisation specification will be stored in a confidential document at BCTU.

Participants randomised by error, i.e. randomised twice or found ineligible according to inclusion/exclusion criteria after randomisation, will be replaced to attain the full sample size.

Following randomisation, a confirmatory e-mail will be sent to the local PI, research nurse/delegated person who randomised the participant. The trial team will also receive a randomisation confirmatory e-mail.

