9.2.2 Secondary outcomes

1. Abstinence from smoking for at least 26 weeks biochemically validated (exhaled CO < 8 ppm) at 52 weeks
2. 7-day point prevalence abstinence from smoking biochemically validated (exhaled CO < 8 ppm) at 52 weeks
3. Self-reported abstinence from smoking for at least 26 weeks at 52 weeks

-
4. Self-reported 7-day point prevalence abstinence from smoking at 4, 26 and 52 weeks
 5. Reduction in cigarettes smoked (self-report of any and > 50% reduction from baseline to 52 weeks, confirmed by reductions in expired CO readings at 52 weeks)
 6. Reduction in cigarettes smoked (self-report of any and > 50% reduction from baseline to 26/52 weeks)
 7. Continued use of allocated product at 4, 26 and 52 weeks
 8. Withdrawal symptoms and urges to smoke (change from baseline to 1/ 2/ 3/ 4 weeks) measured using the mood and physical symptom scale (MPSS)
 9. COPD Symptoms (change from baseline to 4/ 26/ 52 weeks) measured using COPD Assessment Test (CAT) and the Clinical COPD Questionnaire (CCQ)
 10. Number of COPD exacerbations over the past 52 weeks (from baseline to 52 weeks)
 11. Number of self-reported upper respiratory tract infections over the past 52 weeks (from baseline to 52 weeks)
 12. Post bronchodilator spirometry (FEV₁, FVC and MMEF change from baseline to 52 weeks)
 - Forced Expiratory Volume in 1 Second (FEV₁): The maximal volume of air that can be expired in the first second of a forced expiration from a position of full inspiration (measured in Litres (L) and also expressed as the % predicted for age, sex, height and race)
 - Forced Vital Capacity (FVC): The maximal volume of air that can be expired during a forced and complete expiration from a position of full inspiration (measured in L and % predicted)
 - Mean Mid-Expiratory Flow (MMEF): The average flow between 25% and 75% of the FVC manoeuvre (measured in L/sec and % predicted)

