15.2 Analysis of outcomes

A Statistical Analysis Plan (SAP) for the trial will be produced and will provide a more comprehensive description of the planned statistical analyses for the trial. A brief outline of these analyses is given below.

The primary comparison groups will be composed of those randomised to the control treatment (combination NRT and behavioural support) versus those randomised to the intervention (Electronic cigarette and behavioural support). In the first instance, all analyses will be based on the intention to treat principle, i.e. all participants will be analysed in the treatment group to which they were randomised irrespective of adherence or other protocol deviation. For all outcomes, appropriate summary statistics and differences between groups, e.g. mean differences, relative risks will be presented, with 95% confidence intervals and p-values from two-sided tests also given. Outcomes will be adjusted for the minimisation variables listed in section 7.1.1 where possible. No adjustment for multiple comparisons will be made.

15.2.1 *Primary outcome(s)*

The primary outcome for the ECAL trial is smoking abstinence since the TQD biologically validated (exhaled CO<8ppm) at 52 weeks post quit date. This will be measured in accordance with the Russell Standard¹ which is the accepted standard for smoking abstinence in trials of smoking cessation interventions.

The data for this outcome are binary, and therefore will be summarised using the number and percentage of participants in each category by intervention arm. An adjusted relative risk and 95% confidence interval will be estimated from a log-binomial regression model and the p-value from the associated model will be produced and used to determine statistical significance. We will also present the adjusted risk difference and the corresponding 95% confidence interval.

15.2.2 *Secondary outcomes*

The secondary outcomes consist of continuous, binary, and count data types.

Secondary outcomes that are binary in nature will be analysed using the same statistical methods described above for the primary outcome.

Secondary outcomes that are continuous will be summarised using the mean and standard deviation for each intervention arm. Minimum and maximum values will also be presented. The

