difference between the group means and associated 95% confidence intervals at each time-point will be estimated through the use of a repeated measures mixed-effects linear regression model. All post-randomisation assessment times will be included. Parameters allowing for participant, treatment group, time variable, the randomisation minimisation variables and the baseline score will be included (all as fixed effects). Time will be assumed to be a categorical (fixed) variable. To allow for a varying treatment effect over time, a time by treatment interaction parameter will be included in the model. Estimates of differences between groups at each post-randomisation time-point will be taken from the model including this interaction parameter. Results will be presented as an adjusted mean difference and the associated 95% confidence interval. Longitudinal plots of the data over time will be constructed for visual presentation of the data.

Secondary outcomes that involve count data will be analysed using a Poisson regression model (or negative binomial regression if there is evidence of overdispersion) with an offset for the length of time the participant was in the trial included in the model, to obtain an adjusted incidence rate ratio and 95% confidence interval. The p-value from the associated model will be produced and used to determine statistical significance.

Validated questionnaires will be scored using the methods recommended by the authors.

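### No baseline exacerbation count is specified, and the exacerbation count model names none as a covariate: a modest loss of precision in one secondary outcome

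*Protocol*

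**What the plan says.** Section 9.2.2 makes the number of COPD exacerbations to 52 weeks secondary outcome 10 of the randomised comparison.

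Section 15.2.2 analyses counts by Poisson or negative binomial regression "with an offset for the length of time the participant was in the trial included in the model". The covariates come from the general statement in Section 15.2: "Outcomes will be adjusted for the minimisation variables listed in section 7.1.1 where possible". The list itself stands in Section 7.1: COPD stage in two levels, age, sex at birth and nicotine dependence score. For continuous outcomes, Section 15.2.2 goes further: "the randomisation minimisation variables and the baseline score will be included (all as fixed effects".

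Past exacerbations are named before randomisation in one place, the pre-baseline check of Section 4.7.3: "Check if patients have had an COPD exacerbation or inpatient hospital stay within the last 8 weeks". The stated consequence is about booking: "if a patient answers yes to any of these the baseline visit will be made when enough time has passed for them to be eligible". That sentence is attached to a criterion g, which the list does not contain; I read it as the last item, f.

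The baseline questionnaires listed under Table 3 are CAT, HADS, CCQ, EQ-5D-5L and FTND. Section 12.3 places the resource-use questionnaire at 26 and 52 weeks only. Table 3 does schedule a medical history at baseline, without giving its content, and Section 12.2 says that its list of CRFs is not exhaustive.

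**The concern.** The count model allows for overdispersion, that is, for exacerbation rates that differ between patients. To the extent that those differences persist from year to year, a patient's previous count predicts the next one. None of the four minimisation variables is the patient's own exacerbation history; COPD stage is the nearest. If the prior count is left out, the variation it predicts stays in the error term, so the confidence interval for the rate ratio is wider than the same participants could give. A chance imbalance between arms in exacerbation history also goes unadjusted.

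The protocol accepts the principle for continuous outcomes but does not carry it over to this count. The 8-week answer is a poor substitute: it is a yes/no over a short window, and a yes postpones the visit. Section 1.2 says that no e-cigarette trial has been done in COPD, so this by-arm exacerbation estimate will be read with interest even as a secondary result.

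**Working it through.** **The plan's own figure.** The protocol states no power or precision for exacerbations. Its only sample size is for the primary outcome: 8% against 14%, two-sided 5%, 90% power. With a continuity correction this gives 603 per group, as stated in Section 15.1; 1206/0.97 = 1243.3, so 1244, rounded up to 1250. The present point does not touch it.

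**Inputs.**
- From Section 15.1: 625 per arm and 3% loss, so n = 625 × 0.97 ≈ 606 per arm.
- Assumed, because the documents give nothing: mean rate μ of 0.5 to 1.5 per year; negative binomial dispersion k of 0.5 to 1.5; ρ, the share of between-patient variance that is stable from one year to the next, of 0.5 to 0.75.

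**Formulas** (equal rates in both arms, no other covariate).
- Without the prior count: Var₀ = 2(1/μ + k)/n.
- A linear prediction from the prior-year count explains (ρk)²/(k + 1/μ) of k, leaving k₁ = k − (ρk)²/(k + 1/μ), and Var₁ = 2(1/μ + k₁)/n.
- Proportional reduction: 1 − Var₁/Var₀ = [ρk/(k + 1/μ)]². It does not depend on n.

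| Case | μ | k | ρ | Reduction in variance | SE of log rate ratio |
|---|---|---|---|---|---|
| Low | 0.5 | 0.5 | 0.5 | (0.25/2.5)² = 1.0% | 0.0908 to 0.0904 |
| Central | 1 | 1 | 0.5 | (0.5/2)² = 6.25% | 0.0812 to 0.0787 |
| Central | 1 | 1 | 0.75 | (0.75/2)² = 14.1% | 0.0812 to 0.0753 |
| High | 1.5 | 1.5 | 0.75 | (1.125/2.167)² = 27.0% | 0.0846 to 0.0723 |

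In the central case the confidence interval on the log scale becomes 3% to 7% narrower: √(1 − 0.0625) = 0.968 and √(1 − 0.141) = 0.927.

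**Check by simulation.** Negative binomial models were fitted with and without log(prior count + 0.5), 300 replicates per case.
- Central case, ρ = 0.5: variance reduction 5.0% by model SE, 8.4% empirically.
- Central case, ρ = 0.75: 10.6% and 16.2%.
- Low case: 0.9% and −0.2%, in effect nothing.
- High case: 20.2% and 24.6%.

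Neither the formula nor the simulation included COPD stage. The planned model does, so the gain over the planned model would be somewhat smaller than shown.

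**The case against.** The strongest reply is that nothing here is wrong. Section 15.2 calls itself a brief outline and defers to the SAP. It says that outcomes are adjusted for the minimisation variables, not that they are adjusted for nothing else. A medical history is taken at baseline and the CRF fields are not shown, so the count may already be recorded. This is one of twelve secondary outcomes, with no power claimed for it.

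Most of that stands, and it sets the weight of the point. It does not remove it: a SAP can add a covariate only from data that were collected, and what is collected at baseline is settled by the protocol and CRF while recruitment is running.

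Four stronger readings are tempting, and the documents do not support them.
- **That exacerbation history is asked only over 8 weeks.** The protocol is silent on the content of the medical history. What can be said is that no count is specified.
- **That the comparison is biased.** Omitting a prognostic covariate from a randomised comparison costs precision; the comparison stays valid.
- **That the gain is large.** Fully stable patient rates (ρ = 1) would give 25% in the central case and 48% at μ = k = 1.5, but nothing in the protocol supports full stability. A marked rise in power also needs a sizeable by-arm effect. As an illustration, suppose that the arms differ only through the sustained abstinence of Section 15.1 and that quitting abolished every exacerbation. The rate ratio would still be 0.86/0.92 = 0.935. With SEs of 0.081 and 0.075, power would be about 13% and 15%. Smoking reduction or vaping itself could add to the effect, but the protocol gives no figure for it.
- **That recall error is harmless for everyone.** This holds when the value is fixed before allocation. It does not cover values gathered afterwards in an open-label trial (Section 7.2).

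**Conclusion.** The point holds as a missed efficiency in secondary outcome 10. The central estimate is a variance reduction of about 6-14%, with about 1-27% over the assumed range and next to nothing where rates and dispersion are low. All of these figures rest on assumed rates, dispersion and stability, and all are before allowing for COPD stage. The direction is secure; the size is modest and uncertain. It should be treated as a cheap, optional improvement, not as the correction of an error.

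**What to change.** 1. Confirm whether the baseline CRF records the number of COPD exacerbations in the 52 weeks before randomisation, on the same definition as the outcome. If it does not, add that one item.
2. In Section 15.2.2, name this count, for example as log(count + 0.5), as a covariate in the count model for secondary outcome 10, beside the minimisation variables and the offset.
3. For participants already randomised, use only records dated before randomisation, extracted without reference to allocation where possible. Otherwise use a missing-baseline indicator.

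The cost is one CRF item and one model term. The drawbacks are recall error, which shrinks the gain, and a mixed data source (patient report and notes) for those already enrolled. If the count proves to be recorded already, only step 2 remains.
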